This study will use a lifestyle intervention and it is not predicted from the current IGTN study that a standing independent SDMC will be required. If necessary, a plan for convening a SDMC is described in Human Studies (see Appendix).

General analytic plan

Comparability of treatment groups will be performed using the baseline demographic variables (i.e. age, gender, BMI) and relevant prognostic covariants (e.g., HbA1c, autonomic symptoms, and baseline values of primary endpoints). The demographic and prognostic values will be presented by treatment group as means and standard deviations for continuous variables, and analysis of variance will be used to compare the means of the two treatment groups, controlling for baseline. Baseline characteristics will be compared between the study groups. Standard two group comparison methods will be used, such as two sample t-tests for normally distributed variables. Measures of central tendency (means) and variability (standard deviations, ranges) will be estimated. Initial data analyses will allow us to explore the distributions of outcomes studied, may lead to transformation of the dependent variable, and may help identify outlying measures not detected earlier in the data cleaning process.

1) Model check and alternative analysis plans: Model fits will be checked for individual and systematic departures of the observed and fitted values using informal (e.g. inspection of residuals) and formal methods (e.g. based on score tests for extra parameters (104;105). The influence of individual outliers will be evaluated by comparing models with and without outlying values. Outcome variables will be transformed when we cannot fit a parametric model. In our

preliminary data, assumption of normality is reasonable for most outcome variables, including those which are log transformed. Non-parametric analyses e.g. Generalized Additive Models (GAM), (106), or Friedman two-way analysis of variance (105), will be utilized when we cannot fit a parametric model. Outcome measures will be adjusted for baseline by including baseline values as a covariate into the model. As another option, a baseline measure becomes another dependent variable in the repeated measures model and appropriate contrasts will be constructed to adjust for baseline. In computations, SAS PROC MIXED (107), SAS PROC GENMOD, and PROC GAM in SPLUS will be used.

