The key parameter tested in all of these models is the group variable (GRP). The training efficacy hypotheses will be tested by comparing two nested models with and without GRP. The outcome at baseline and gender, BMI and Age variables are included to adjust the primary outcome for its baseline value. Assuming that residuals from the model fit are normally distributed, the analysis is equivalent to a classical analysis of covariance. For outcomes that do not fit a normal distribution, inverse, logarithmic or power transformations will be performed or generalized linear models (GLM) (110) with Poisson or gamma error will be considered. Since the outcomes are measured on three occasions (baseline, 6 months and 12 months), a model that takes into account repeated measures will be developed in the framework of linear mixed effects models (LME) or generalized linear mixed effects models (GLMM). Models for repeated measures will yield three tests: 1) a test for outcome changes over time of the study (time effect); 2) a test of group differences (an intervention effect); and 3) a test for interaction of intervention effect with time. We are primarily interested in the overall intervention effect. However, a changing intervention effect over time as reflected in an intervention by time interaction is of great interest since it might suggest that the intervention has a greater impact as time progresses.

Additional data analyses

A number of additional key variables will be assessed in order to investigate the maintenance of PA and 6MW improvement and mechanisms underlying the changes in neuropathy progression and mobility function.

Tertiary hypothesis (Maintenance of 6MW and PA at 12 months): At 12 months compared to 6 months, and compared to SC, TDPA participants will show greater sustained improvement in 6MW and self-reported PA.

Exploratory/mechanistic hypothesis: Improvement in measures of neuropathy (NCS, MDNS, IENFD), mobility function and PA will correlate strongly with each other and with improvement in specific measures of metabolic function and weight loss

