We will rely on regression models to study multivariate relationships. These hypotheses will be addressed by examining the extent to which change in one of these measures relates to each other when controlling for other factors. Models can utilize outcome measurements at all time points (baseline, 6 months, and 12 months). We can also consider a number of measurements as contributing factors, i.e. covariates. For longitudinal data, models of the following type will be considered: (VS=Variables used in minimization; BA=outcome at Baseline; GRP=intervention group; COV= one or more covariates; TIME= time variable; *=interaction between variables):
Outcome at 6 and 12 months = VS + BA + GRP + COV + GRP*TIME + COV*TIME

The key aspects of this model in the context of our tertiary hypotheses are interactions GRP*TIME and COV*TIME, and the magnitude and significance of these interaction effects provide insight into mechanisms underlying study group differences. The remaining terms are used in the model to reflect study design and adjust for baseline values. The following methods will be considered particularly when analyzing longitudinal data for post-intervention hypotheses: LME models for continuous variables with normally distributed residuals); GLMM (111), and SAS PROC/GLMMIX (112). Both of these methods allow for unbalanced data, time-varying covariates, and structured covariance matrices. For the 12 month outcome, the model can take into account repeated measures and as such will be developed in the framework of LME or GLMM.

These exploratory analyses will not provide a definitive mechanism underlying changes in neuropathy progression, mobility function, or PA but we will be able to determine which variables are more strongly correlated and potentially more physiologically related. Our sample size of 64 per group (which should be achievable because we will recruit more people based on drop-out, as previously discussed) allows

us to detect effects of variables and/or their interactions as low as 5-6% of the variance explained over and above other predictors with alpha=0.05 and power of 80%.

Table 5: Summary of Variables

Variable	Type	Time		
		Baseline	6 months	12 months
Age, Gender, BMI	Minimization variables			
6MW	Dependent (Primary)	X	X	X
IENFD	Dependent (Secondary)	X		X
CHAMPS	Dependent (Secondary)	X	X	X
Measures of progression: MDNS	Covariates	X	X	X
Electrophysiological measures of progression: NCS	Covariates	X	X	X

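### Does the repeated-measures model dilute the treatment effect by counting baseline as one of its outcome visits?

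*Combined protocol and SAP*

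**What the plan says.** The Hypothesis testing plan tests 6MW and physical activity (PA) at 6 months by regressing the 6-month value on its baseline, gender, BMI, age and group. Intraepidermal nerve fiber density (IENFD) is tested the same way at 12 months. The group term is the key parameter in each.

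The same section then adds a mixed model. Its reason is: "Since the outcomes are measured on three occasions (baseline, 6 months and 12 months), a model that takes into account repeated measures" should be developed. The model is to give three tests: change over time, "a test of group differences (an intervention effect", and the group-by-time interaction. The plan continues "We are primarily interested in the overall intervention effect", and the interaction matters because "it might suggest that the intervention has a greater impact as time progresses". No equation or contrast is given at this point.

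Two other places deal with baseline:

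- General analytic plan, item 1 (model check and alternative analyses): "Outcome measures will be adjusted for baseline by including baseline values as a covariate into the model". As an alternative, "a baseline measure becomes another dependent variable in the repeated measures model and appropriate contrasts will be constructed to adjust for baseline".
- Additional data analyses: "Models can utilize outcome measurements at all time points (baseline, 6 months, and 12 months", followed by the one longitudinal equation in the document, "Outcome at 6 and 12 months = VS + BA + GRP + COV + GRP*TIME + COV*TIME". BA is the baseline outcome and VS the minimization variables. The group-by-time term is named there as a key term for the tertiary hypotheses.

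**The concern.** A reader who takes the three occasions as the model's outcome visits sees a familiar error. Allocation follows baseline testing, so the expected group difference at baseline is zero. A group test over all three visits averages that zero in and understates the benefit. The treatment effect then appears as a group-by-time interaction even when the benefit is identical at 6 and 12 months, because the groups part after baseline. Ranking the group test first and reading the interaction as possible growth would both be mistaken for that model.

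At stake would be the supplementary results for 6MW and PA. A fully maintained benefit could show a non-significant overall effect beside a significant interaction, and be described as increasing with time. That bears on the tertiary question of whether improvement is sustained to 12 months. The mention of three occasions is also inexact for IENFD, which Table 5 shows at baseline and 12 months only.

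**Working it through.** **Inputs.** From the sample size section: 6MW difference 50, baseline-adjusted SD 97, 64 per group, two-sided alpha 0.05, power 80%. The correlation between visits, rho, is not given. It is assumed equal for all pairs of visits and varied from 0.3 to 0.9.

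**1. The plan's own figure.** n per group = 2(1.960 + 0.842)²/d².

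| d | Normal formula | t-based |
|---|---|---|
| 0.50 | 63 | 64 |
| 0.51 (as tabulated) | 61 | 62 |
| 50/97 | 60 | 61 |

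The stated 64 is reproduced at d = 0.50 and is slightly conservative for 50/97. It belongs to the 6-month regression, whose power at 64 per group is 0.83 (normal approximation).

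**2. Baseline as an outcome, plain group test.** Take true differences of 0, 50 and 50.

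- Estimate: (0 + 50 + 50)/3 = 33.3, whatever the correlation.
- Unadjusted SD: s = 97/√(1 − rho²). At rho = 0.6, s = 97/0.8 = 121.2.
- Standard error: s√((1 + 2rho)/3) × √(2/64) = 103.8 × 0.177 = 18.4.
- z = 33.3/18.4 = 1.81, so power is 0.44.

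**3. Interaction in that same model (2 df).** Noncentrality = (n/2) Σ(difference − mean)²/[s²(1 − rho)]. At rho = 0.6 this is 32 × 1666.7/(121.2² × 0.4) = 9.07, giving power 0.77.

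**4. Baseline as covariate, outcomes at 6 and 12 months.**

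- Estimate of the average group effect: (50 + 50)/2 = 50.
- Residual correlation between the two visits: rho/(1 + rho) = 0.375 at rho = 0.6.
- SD of the two-visit mean: 97√((1 + 0.375)/2) = 80.4; standard error 80.4 × 0.177 = 14.2.
- z = 50/14.2 = 3.52, so power is 0.94.
- The interaction now compares 6 with 12 months and rejects 5% of the time when the effect is constant.

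**5. Range over rho (constant difference of 50).**

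| rho | Group test, three visits | Interaction, three visits | Group test, baseline as covariate |
|---|---|---|---|
| 0.3 | 0.72 | 0.68 | 0.96 |
| 0.5 | 0.54 | 0.75 | 0.95 |
| 0.6 | 0.44 | 0.77 | 0.94 |
| 0.7 | 0.34 | 0.80 | 0.94 |
| 0.8 | 0.24 | 0.82 | 0.93 |
| 0.9 | 0.14 | 0.85 | 0.93 |

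A simulation of 4,000 trials at rho = 0.6 gave 0.44 for the three-visit group test, 0.76 for its interaction, 0.05 for the 6-versus-12-month interaction and 0.81 for the 6-month regression.

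**6. Baseline as an outcome, with a contrast.** The contrast that adjusts for baseline, the group difference in mean change, estimates (50 + 50)/2 − 0 = 50. The dilution disappears.

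**7. Which of these the plan describes.** The dilution in steps 2 and 3 needs two things together: baseline as an outcome, and a plain group test with no contrast. The General analytic plan excludes that pair. Its default is step 4, and its alternative is step 6. The written equation is of the step 4 type. The sentence about three occasions reports when data are collected, and that does not fix baseline's place in the model. The equation is shorthand: it has no separate time term, but a time effect is the first of the three tests listed, so an analyst would include it.

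**The case for a change.** The best argument for a change is that three sections leave more than one model open. The three occasions are given as the very reason for the model, so the natural reading is that all three are outcomes. The written equation is of a type that is only to be considered, and the sentence before it speaks of using all time points. If baseline is an outcome, the correct contrast belongs with the interaction, whereas the plan puts the group test first. A cross-reference would cost a few words, and the loss of power in the wrong model is large.

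Part of this stands. Baseline's role is not stated where the repeated-measures model is introduced, and the arithmetic for the undesirable model is correct. The rest is weaker. Using all time points is compatible with an equation in which baseline enters as a covariate. A test of group differences can be a post-baseline contrast, since nothing specifies an unconstrained factorial model with a bare main effect. The remark about growing impact is hedged, and it is valid under the written equation. The maintenance question is tied to the group-by-time term in that equation, where a constant effect gives 5% rejections. For IENFD, the plan assigns a 12-month regression and nowhere proposes averaging baseline with 12 months.

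**Conclusion.** No change follows. The one-third dilution (33.3 instead of 50) is real for a model that the plan does not set out and that its general rules on baseline exclude. Its size needs no assumed correlation. The power figures do: they assume equal correlation between visits and a difference of 50 at both follow-up visits, and over rho 0.3 to 0.9 the three-visit group test ranges from 0.72 down to 0.14.

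Read as a whole, the plan gives a sound 6-month test for 6MW and PA, a sound 12-month test for IENFD, and a longitudinal equation whose group and interaction terms mean what the text says. The gap is one missing detail in a supplementary model. A statistician following the General analytic plan and the written equation would fill it correctly. This rests on the analyst applying those two sections together.

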Metabolic measures: Glucose, Lipids, HgbA1c	Covariates	X	X	X
Mobility function measures: Unipedal stance, TRE, 6MW, and gait speed	Covariates	X	X	X

Rationale regarding potential limitations to planned protocol

1) Use of single combined diet-PA intervention versus factorial design: We considered a four group factorial design, comparing diet only, PA only, combined diet-PA, and usual care. There are a number of problems with this design. Firstly, diet interacts with PA and this likely occurs in a non-additive but multiplicative manner. This interaction may depend on weight loss as well, which results from both diet and possibly PA interventions, further complicating the study interpretation. Secondly, in order for the factorial design to be properly tested, the diet group must not increase PA and the PA group must not diet. This may be theoretically scientifically valid but operationally not practical. While the proposed Standard Care group may or may not change their diet, increase their PA or lose weight, at least we will know the effect of the use of a standard set of recommendations, and, subsequently, the incremental benefits of a tailored combined diet-PA enhancement program. Finally, given the literature supporting the benefits of diet and PA interventions in reducing the progression of IGT (4;26;27), a more valid program to translate into the community should at least attempt elements of each. Often the initial evaluation may include several components, to be determined in later studies in a factorial design. In this case, such a design appears ill-advised and impractical.

2) Center-based group PA program versus home-based program: We are experienced in providing both center-based and home-based programs. Given the wide geographical distribution of the participants, a center-based program, even once per week, is not possible. The home-program is somewhat of a misnomer, in that TDPA participants are encouraged (and provided support) to enhance their PA in whatever manner they would prefer. This could include participation in a local center-based group program at a center of their choice.

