3) PA program with an additional walking and balance program: The addition of the walking and balance program in particular is critical to address what we believe to be basic impairments in walking endurance and standing balance in patients with IGR. We understand that this addition will also complicate interpretation of the results, i.e. the effect of a PA program alone will be unclear, although the interpretation is already complicated by addition of a diet component. Future studies may consider deleting this supplement and testing the effect of the PA program alone, although PA programs in general tend to include walking anyway.

4) Lack of a “true” control group: While scientifically valid, a control group with no diet or PA intervention whatsoever is both unrealistic and unethical, given the present guidelines for those with IGR and promulgation of diet and PA suggestions in general. The control group must also receive a control “intervention” (health education follow-up) for the added “attention” provided to the intervention group. It is also likely that the effect of the proposed intervention would have been greater had the control group not participated in any follow-up (as in the usual care scenario), and this should be acknowledged in the interpretation of the study outcome.

5) Compliance with long term biopsy and intervention adherence: We are experienced in providing long-term follow up in diet, exercise, biopsies (IGTN study), and PA interventions. We believe that given the incentives provided, the proposed attrition rate, and the intrinsic value

provided in both intervention groups, the proposed plan is feasible and will likely lead to the expected outcomes.

6) Minimization variables: Use of a minimization technique to allocate participants to experimental groups leads to group equivalence in key variables including age, gender, and BMI. Other variables that might be considered for minimization include a measure of functional status (such as gait speed or neuropathy impairment level) and a measure of diabetes status (such as fasting glucose, HgbA1c, or time since diagnosis of diabetes). We were limited in the number of minimization variables allowed and thus chose what we believed to be the most crucial variables. We will nevertheless include all of these variables in the tertiary and exploratory analyses.

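### One equation serves both the tertiary maintenance test and the mechanism analysis, and its covariates are not limited to baseline values

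*Combined protocol and SAP*

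**What the plan says.** The tertiary hypothesis is a comparison of the randomized arms: "At 12 months compared to 6 months, and compared to SC, TDPA participants will show greater sustained improvement in 6MW and self-reported PA". Under Additional data analyses it is stated next to the exploratory/mechanistic hypothesis, and the two are then addressed together. The plan announces that "models of the following type will be considered" and gives "Outcome at 6 and 12 months = VS + BA + GRP + COV + GRP*TIME + COV*TIME". It adds: "The key aspects of this model in the context of our tertiary hypotheses are interactions GRP*TIME and COV*TIME".

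BA is defined as the baseline outcome. COV is defined only as one or more covariates, with no time point. On their use the section says "We can also consider a number of measurements as contributing factors, i.e. covariates", and of the fitting methods it says "Both of these methods allow for unbalanced data, time-varying covariates, and structured covariance matrices".

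Table 5 types several groups of variables as covariates: MDNS, NCS, the metabolic measures (glucose, lipids, HbA1c) and "Mobility function measures: Unipedal stance, TRE, 6MW, and gait speed". Each is marked at baseline, 6 and 12 months. 6MW therefore appears both as a dependent variable and as a covariate.

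The Hypothesis testing plan gives the primary and secondary models with baseline outcome, gender, BMI, age and group only. It also outlines a repeated-measures model with tests for time, group and their interaction, and no COV term. No sentence says which of the two longitudinal models decides the tertiary hypothesis.

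**The concern.** TDPA consists of graded walking, balance exercises and a weight-loss diet. Gait speed, balance, glucose and HbA1c are variables such a programme is meant to move, and the 6MW description under Measures of mobility function says 6MW is correlated with gait speed and balance. Their values at 6 and 12 months are therefore likely to be both affected by assignment and related to the outcome.

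With such values in the model, the group terms describe what is left of the TDPA-SC difference after part of TDPA's own route to benefit is held fixed. That is not the effect of being assigned to TDPA, and randomization no longer protects the comparison, because people with the same on-treatment gait speed in the two arms need not be alike otherwise.

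The rationale for the tertiary hypothesis treats sustained improvement as a critical question. As written, an analyst could use no covariate, baseline covariates or on-treatment covariates, make that choice after seeing the data, and reach materially different answers.

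**Working it through.** **The plan's own figure for these models.** The plan says 64 per group can detect 5-6% of variance explained at alpha 0.05 and 80% power. For one added 1-df term with N = 128 and noncentrality N·R²/(1−R²), the smallest partial R² with 80% power is 5.9% (power 73% at 5% and 81% at 6%). The figure reproduces. It concerns whether a term can be detected, not what the GRP term means once COV is in the model.

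**Inputs from Sample size calculation.** 6MW difference 50, baseline-adjusted SD 97, 64 per group. The table gives no unit. Without COV, SE = 97 × √(2/64) = 17.1, 50/17.1 = 2.92, and power = Φ(2.92 − 1.96) = 83%. The plan sized this at 6 months; using 50 and 97 at 12 months is an assumption.

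**Inputs the documents do not give (assumed, shown as a range).** d is the TDPA effect on the covariate in SD units. r is the correlation of covariate and 6MW residuals within arm.

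**12-month difference with on-treatment COV.** Adjusted difference = 50 − 97·r·d. Its SE = 97·√(1−r²)·√(2/64)·√(1+d²/4).

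| d | r | Difference remaining | Share kept | Approx. power |
|---|---|---|---|---|
| 0 | any | 50 | 100% | 83% or more |
| 0.25 | 0.3 | 50 − 7.3 = 42.7 | 85% | 74% |
| 0.25 | 0.7 | 50 − 17.0 = 33.0 | 66% | 76% |
| 0.5 | 0.3 | 50 − 14.6 = 35.5 | 71% | 56% |
| 0.5 | 0.5 | 50 − 24.3 = 25.8 | 52% | 39% |
| 0.5 | 0.7 | 50 − 34.0 = 16.1 | 32% | 25% |
| 0.5 | 0.9 | 50 − 43.7 = 6.4 | 13% | 13% |

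A simulation of 400 trials per setting, with a TIME main effect added to the written equation, agrees. At d = 0.5 and r = 0.7 the 12-month estimate is 50.2 without COV and 16.2 with time-varying COV. With COV fixed at baseline it stays at 50.2, as randomization implies.

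**GRP×TIME.** COV*TIME lets the covariate slope differ by visit, so the formula applies at each visit separately. Take r = 0.7.

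- Benefit fully sustained (50 and 50, d = 0.5 at both visits): (50 − 34.0) − (50 − 34.0) = 0. Without COV it is also 0.
- Benefit halved by 12 months (50 then 25, d = 0.5 then 0.25): true interaction 25 − 50 = −25. Adjusted: (25 − 17.0) − (50 − 34.0) = 8.0 − 16.0 = −8.0. The simulation gives −23.8 without COV and −6.2 with it; the gaps from −25 and −8.0 are consistent with simulation noise.

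On-treatment adjustment thus shrinks the 12-month difference. It leaves GRP×TIME alone when benefit is sustained, and it masks most of a loss when benefit wanes.

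**The case against.** A reader might infer that the plan commits to adjusting for on-treatment covariates and so removes the very benefit it sets out to test. The documents do not support that.

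- The equation is a type of model to be considered and covariates are optional. The sentence on time-varying covariates states what the methods can handle, not how COV will be coded. Table 5 shows when variables are measured, not which value enters which model.
- The section says the terms other than the two interactions reflect the design and adjust for baseline, which leans towards a baseline COV.
- The statement "We will nevertheless include all of these variables in the tertiary and exploratory analyses", in the limitations item on minimization variables, follows a list of candidate minimization factors, gait speed among them. Such factors must be known before allocation, so baseline use is the natural reading there.
- A COV-free repeated-measures model is already described for outcomes measured three times. Among the dependent variables in Table 5, only 6MW and CHAMPS fit that description, and these are the tertiary outcomes.
- Some covariates may hardly move. The preliminary data report less change in NCS and suggest large-fiber recovery may take longer than a year. With no shift there is no attenuation.
- The power figures above belong to the 12-month group difference, not to GRP×TIME, the group term named as key.

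All of this stands, and it limits how strongly the point can be put. It does not dispose of it. The COV-free model is placed with the primary and secondary tests and is never assigned to the tertiary hypothesis, whereas the COV equation is tied to that hypothesis in so many words. The stated purpose of its interactions, insight into how the arms come to differ, makes sense mainly for on-treatment values, because a baseline value cannot mediate a treatment effect.

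**Conclusion.** The concern holds in a conditional form. The plan does not separate the maintenance test from the mechanism model and does not fix COV at baseline. If post-randomization values are used, GRP and GRP×TIME do not estimate the effect of assignment to TDPA.

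The size cannot be settled from the documents. With an assumed effect of 50 and SD 97, the share kept runs from 100% (no shift, or no correlation) to 13% (0.5 SD shift, r = 0.9), so to say that the benefit is removed would describe only the extreme. A waning of 25 could show as about 8 at r = 0.7. If the benefit is fully sustained, GRP×TIME is about 0 either way.

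Only the tertiary hypothesis is touched, and the plan ranks it below the primary and secondary ones, whose models use baseline terms only. Severity is low to moderate.

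**What to change.** Name the deciding model for the tertiary hypothesis: the COV-free repeated-measures model already outlined in the Hypothesis testing plan, written as VS + BA + GRP + TIME + GRP×TIME, with the 12-month TDPA-SC contrast reported beside the interaction. The TIME main effect should be explicit, since the present equation omits it.

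Allow any added Table 5 covariate only at its baseline value, and state that no post-randomization variable enters a model used for a TDPA-SC effect. Keep on-treatment covariates in the exploratory mechanism models, with a sentence that GRP there is not read as the treatment effect.

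The cost is SAP wording. No data are added, and every planned mechanism analysis is kept.

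### COV*TIME, named as a key mechanism term, does not test whether improvement tracks improvement; the exploratory model needs a change-in-covariate term, a TIME main effect and a separate 12-month form for IENFD

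*Combined protocol and SAP*

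**What the plan says.** The exploratory hypothesis is that improvement in neuropathy, mobility function and PA "will correlate strongly with each other and with improvement in specific measures of metabolic function and weight loss". The section on additional data analyses gives the method as "examining the extent to which change in one of these measures relates to each other when controlling for other factors". This serves Specific Aim 2.

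One longitudinal formula is printed: "Outcome at 6 and 12 months = VS + BA + GRP + COV + GRP*TIME + COV*TIME". BA is the baseline of the outcome only. COV is defined as one or more covariates, without saying whether it is a follow-up level, a baseline value or a change. The two interactions are called the key aspects, in the context of the tertiary hypotheses, and the sentence adds that "the magnitude and significance of these interaction effects provide insight into mechanisms underlying study group differences". The remaining terms are described as reflecting the design and adjusting for baseline.

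The hypothesis testing plan introduces repeated-measures models with the words "Since the outcomes are measured on three occasions (baseline, 6 months and 12 months", and makes no exception for IENFD. The description of IENFD, the study schedule and Table 5 all place biopsy at baseline and 12 months only. Table 5 lists "Metabolic measures: Glucose, Lipids, HgbA1c" as covariates but no weight. BMI appears there only as a minimization variable, although the schedule has weight measured at screening, 6 and 12 months.

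**The concern.** The question is whether change goes with change. The term singled out for mechanism answers another question: whether an association is stronger at one follow-up visit than at the other. A team following the text could see a null COV*TIME and conclude that a metabolic measure plays no part when its change tracks the outcome closely. The team could also see a significant COV*TIME that reflects only a trend in the outcome, because the formula has no TIME main effect. If COV is entered as a follow-up level, its own coefficient can be significant merely because patients who start high on the covariate differ on the outcome. For IENFD, the neuropathy endpoint, the printed terms cannot all be estimated, and the 12-month IENFD model in the hypothesis testing plan has no covariate. At stake is the answer to Specific Aim 2.

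**Working it through.** **1. The plan's own figure.** The section states that 64 per group detects 5–6% of variance at alpha 0.05 and 80% power. By normal approximation, (1.960 + 0.842)² = 7.85, and 7.85/(128 + 7.85) = 5.8%. The noncentral F test with 1 df gives 5.9%, with power of 73% at 5% and 81% at 6%. The figure reproduces. The sample size is not in question; the issue is which term the power is spent on.

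**2. What COV*TIME measures.** Let the covariate slope be s6 at 6 months and s12 at 12 months. In the formula, slope = β + γ·TIME, so γ = (s12 − s6)/6. If s6 = s12, then γ = 0 however large the common slope is.

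**3. What the COV coefficient measures if COV is a follow-up level.** Write the level as C0 + D (baseline plus change), with true coefficients b0 and b1. One coefficient must serve both. With C0 and D uncorrelated it is approximately (b0·Var C0 + b1·Var D)/(Var C0 + Var D), with variances taken after adjustment for BA.

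**4. Illustration.** The effect sizes are assumptions, since the documents give none. Settings: 128 patients, visits at 6 and 12 months, TIME main effect added, covariate SD 1 at baseline, SD of change 0.6 at 6 months, patient-clustered standard errors, 2000 runs.

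| Truth | Coding of COV | COV coefficient, mean (significant) | COV*TIME significant |
|---|---|---|---|
| A. Change slope 0.5, equal at both visits | level only | 0.13 (58%) | 8% |
| A | change from baseline | 0.50 (about 99%) | 6% |
| A | level plus baseline | 0.50 (over 99%) | 5% |
| B. No change link, baseline correlation 0.5 | level only | 0.08 (27%) | 6% |
| B | change from baseline | 0.00 (6%) | 6% |
| B | level plus baseline | 0.00 (6%) | 6% |

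Step 3 reproduces row A, level only: 0.5 × 0.36/(1 + 0.36) = 0.13. A separate run of case A rejected COV*TIME in 4% of trials and the change-in-COV coefficient in 100%. A simpler set-up, with one follow-up, no group term, change irrelevant and a baseline slope of 0.2, gave a significant level-only coefficient in 30–65% of trials for within-person correlations of 0.5–0.8. With baseline COV added the rate was 4–6%. Baseline slopes of 0.1–0.3 widen the level-only range to 11–94%, so the size depends on the assumption.

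**5. No TIME main effect.** Suppose the outcome drifts by δ between visits in both groups and the covariate slope is constant. The drift must be absorbed by the only terms that contain TIME. With GRP coded 0/1 and COV far from zero relative to its spread, COV*TIME takes it up. With COV centred at zero, GRP*TIME does. With a drift of 0.2 (baseline SD 1) and an uncentred covariate, COV*TIME was significant in 55% and 60% of trials in two runs, although the slope did not differ between visits.

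**6. IENFD.** There is one post-baseline value, so TIME = 12 in every row, and GRP*TIME = 12·GRP and COV*TIME = 12·COV. The columns are intercept, three VS, BA, GRP, COV and the two interactions: 9 columns, rank 7. Without the TIME terms there are 7 columns and rank 7, which is estimable. When IENFD is the covariate, it likewise has no 6-month value.

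**The case against.** The plan is more careful than a quick reading suggests.

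- A reader might infer that the model enters covariate levels without their baselines. The documents do not say so. COV is undefined, and the lead sentence speaks of change. Item 6 of the rationale on limitations says that gait speed, neuropathy level, fasting glucose, HbA1c and time since diagnosis will be included in the tertiary and exploratory analyses. The natural reading is baseline values. This stands for those variables, but the formula does not show their baselines, and it leaves lipids, TRE and weight open.
- A reader might infer that the model cannot show that improvement tracks improvement. It can: the COV coefficient is in the formula and tests exactly that when coded as change (case A). The plan just does not name it as the test.
- The key-terms sentence is tied to the tertiary hypotheses. For maintenance from 6 to 12 months, GRP*TIME is the right term. This stands for GRP*TIME, but the same sentence also draws mechanism insight from COV*TIME.
- The 4–8% rejection of COV*TIME might be read as lack of power. It is not. The true interaction was zero, so this is the type I error rate; it shows that the term addresses a different question.
- The missing TIME main effect may be shorthand, since the hypothesis testing plan lists a time effect among its repeated-measures tests. That is possible, but the printed formula should say so.
- The formula is only a type to be considered for longitudinal data, and IENFD has its own 12-month model for the group effect. With one follow-up an analyst would drop TIME. That is true, but no IENFD model with a covariate is written down.
- The plan gives mechanism tests less weight and disclaims a definitive mechanism. This limits the consequence.

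**Conclusion.** The concern holds in a limited form. COV*TIME does not test the change-on-change hypothesis and should not be read as a mechanism test. That follows from algebra and needs no assumed effect, as does the rank deficiency for IENFD. The printed formula lets a time trend leak into the interactions. If COV is a follow-up level, its coefficient mixes stable differences between patients with change. That last point is conditional on a coding the plan does not state. The rejection rates (27% against about 6% for a level-only covariate, and 55–60% for the leaked trend) are illustrative and move with the assumed effects. The consequence is confined to exploratory Specific Aim 2. The documents give no ground for extending it to the primary or secondary comparisons, which use separate models without COV, or to the sample size. The change is worth making because a stated rule of interpretation can give the wrong answer and the data for the right one are already collected.

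**What to change.** Keep GRP*TIME, with a TIME main effect, for the tertiary maintenance hypothesis; replacing the whole equation would lose that test. Add a separate exploratory model:

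- **Outcomes with two follow-ups:** outcome at visit = VS + BA + GRP + TIME + GRP*TIME + baseline COV + change in COV.
- **IENFD, as outcome or covariate:** 12 months only, without TIME and GRP*TIME.
- **Test:** name the change-in-COV coefficient as the test of the mechanism hypothesis, reported as an exploratory association.
- **COV*TIME:** if reported at all, describe it as a difference in slope between visits, not as evidence on mechanism.
- **Text:** state that IENFD is an exception to the three measurement occasions, and list change in weight among the covariates in Table 5.

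The cost is SAP wording and one or two extra degrees of freedom per covariate. The baselines and the 6- and 12-month weights are already in the schedule, so no visits, tests or patients are added.
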